Appendix E. West Haven Criteria

<http://www.mdcalc.com/hepatic-encephalopathy-grades-stages/>

Grade of Hepatic Encephalopathy	Description	Suggested Operative Criteria
Grade I	
• Trivial lack of awareness• Euphoria or anxiety• Shortened attention span• Impairment of addition or subtraction• Altered sleep rhythm	Despite oriented in time and space (see below), the subject appears to have some cognitive/ behavioral decay with respect to his or her standard on clinical examination or to the caregivers
Grade II	
• Lethargy or apathy• Disorientation for time• Obvious personality change• Inappropriate behavior• Dyspraxia• Asterixis	Disoriented for time (at least three of the followings are wrong: day of the month, day of the week, month, season, or year) ± the other mentioned symptoms
Grade III	
• Somnolence to semi stupor• Responsive to stimuli• Confused• Gross disorientation• Bizarre behavior	Disoriented also for space (at least three of the following wrongly reported: country, state [or region], city, or place) ± the other mentioned symptoms
Grade IV	
• Coma	Does not respond even to painful stimuli

Source: Vistrup H, AModio P, Bajaj J, Cordoba J, Ferenci P, Mullen KD et al. Hepatic encephalopathy in chronic liver disease: 2014 Practice Guideline by the American Association for the Study of Liver Diseases and the European Association for the Study of the Liver. Hepatology. 2014;60(2):715–35

11.3 Appendix 3: Schedule of Assessments – Long-Term Follow-Up.....	59

List of Tables

Table 1 Approach for Intercurrent Events for the Primary Endpoint at Week 24 ..	14
Table 2 Data Review to Identify Important Protocol Deviations.....	18
Table 3 Summary of Outcome Variables and Analysis Sets.....	19
Table 4 Summary of Subgroup Analysis.....	42
Table 5 Clinical Laboratory Assessments	47
Table 6 Laboratory Toxicity Grade Criteria of Selected Clinical Laboratory Assessments	48

CONFIDENTIAL

Document Date: 07 Feb 2024

Page 5 of 60

ST-AD-008 version 05

Statistical Analysis Plan

Sponsor Name: Akero Therapeutics, Inc.
Sponsor Protocol ID: AK-US-001-0102

Reviewers

The following reviews of the SAP were conducted:

Statistical Analysis Plan

Sponsor Name: Akero Therapeutics, Inc.
Sponsor Protocol ID: AK-US-001-0102

Glossary of Abbreviations

Abbreviation	Term
ADA	anti-drug antibodies
AE	adverse event
AESI	adverse event of special interest
ALP	alkaline phosphatase
ALT	alanine aminotransferase (SGPT)
ANCOVA	analysis of covariance
Apo	Apolipoprotein
AST	aspartate aminotransferase (SGOT)
ATC	anatomical therapeutic chemical
BLQ	below limit of quantification
BMD	Bone Mineral Density
BMI	body mass index
CAP	controlled attenuation parameter
CI	confidence interval
CLDQ	Chronic Liver Disease Questionnaire
CMH	Cochran-Mantel-Haenszel
COVID-19	Coronavirus-19 infection
CP	Child-Pugh
CRN	Clinical Research Network
CTCAE	Common Terminology Criteria for Adverse Events
CV	coefficient of variation
DILI	drug-induced liver injury
DMC	Data Monitoring Committee
DXA	Dual Energy X-ray Absorptiometry
ECG	electrocardiogram
eCRF	electronic Case Report Form
edISH	evaluation of drug-induced serious hepatotoxicity
EFS	event-free survival
EFX	efruxifermin
ELF	Enhanced Liver Fibrosis Panel
EOS	End of Study
ET	Early Termination
FAS	full analysis set
US FDA	United States Food and Drug Administration
FGF21	fibroblast growth factor 21
GGT	gamma glutamyl transferase
H	high
HbA1c	hemoglobin A1c
HDL-C	high-density lipoprotein cholesterol
HE	hepatic encephalopathy
HLGT	high-level group term
HLT	high-level term
HOMA	homeostasis model assessment of insulin resistance, (HOMA-IR) and beta cell function (HOMA-B)
INR	International Normalized Ratio
IQR	interquartile range
kPa	kilopascal

CONFIDENTIAL

Statistical Analysis Plan

Sponsor Name: Akero Therapeutics, Inc.
Sponsor Protocol ID: AK-US-001-0102

Abbreviation	Term
L	low
LBAS	liver biopsy analysis set
LDL-C	low-density lipoprotein cholesterol
LDL-P	low-density lipoprotein particle
LLN	lower limit of normal
LLOQ	low limit of quantification
LLT	low-level term
Lp	Lipoprotein
LS	least square
LSM	liver stiffness measurement
MedDRA	Medical Dictionary for Regulatory Activities
MELD	Model for End-Stage Liver Disease
MFAS	Modified Full Analysis Set
MMRM	mixed-model repeated-measures
MRI	magnetic resonance imaging
MRI-PDFF	magnetic resonance imaging – proton density fat fraction
NAb	neutralizing antibody
NAFLD	non-alcoholic fatty liver disease
NAS	non-alcoholic fatty liver disease activity score
NASH	nonalcoholic steatohepatitis
NCI	National Cancer Institute
NMR	nuclear magnetic resonance
PK	pharmacokinetics
PPS	per-protocol set
Pro-C3	N-terminal Type III Collagen Propeptide
PT	preferred term
QTcF	Fridericia corrected QT interval
QW	every week
SAE	serious adverse event
SAP	Statistical Analysis Plan
SD	standard deviation
SOC	system organ class
T2D	type 2 diabetes
TB	Total bilirubin
TEAE	treatment emergent adverse event
TESAE	treatment-emergent serious AE
TFLs	tables, figures and listings
ULN	upper limit of normal
WHO	World Health Organization

CONFIDENTIAL

Statistical Analysis Plan

Sponsor Name: Akero Therapeutics, Inc.
Sponsor Protocol ID: AK-US-001-0102

1. Source Documents

The Statistical Analysis Plan (SAP) was written based on the following documentation:

Document	Date	Version
Protocol	18 Apr 2022	Amendment 4
eCRF	17 Aug 2021	PROD 3.0

This SAP describes listings, summaries, and analyses of data collected from Screening through the Week 24 visit or Early Termination, the 30-Day Follow-up visit, and also during long-term follow-up through Week 96 of subjects enrolled in this Phase 2b study.

2. Protocol Details

2.1 [REDACTED]

CONFIDENTIAL

Statistical Analysis Plan

Sponsor Name: Akero Therapeutics, Inc.
Sponsor Protocol ID: AK-US-001-0102

2.1.3 [REDACTED]

For more information, contact the Office of the Vice President for Research and Economic Development at [contact] or [contact].

A horizontal bar chart illustrating the percentage of respondents who have heard of various terms. The y-axis lists the terms, and the x-axis represents the percentage, ranging from 0% to 100% in increments of 10%. The bars are black and are separated by small gaps.

Term	Percentage
Healthcare	98%
Medical	95%
Health	92%
Healthcare system	90%
Medical system	88%
Healthcare reform	85%
Medical reform	82%
Healthcare insurance	80%
Medical insurance	78%
Healthcare technology	75%
Medical technology	72%
Healthcare policy	70%
Medical policy	68%
Healthcare access	65%
Medical access	62%
Healthcare equity	60%
Medical equity	58%
Healthcare disparities	55%
Medical disparities	52%
Healthcare quality	50%
Medical quality	48%
Healthcare cost	45%
Medical cost	42%
Healthcare resources	40%
Medical resources	38%
Healthcare delivery	35%
Medical delivery	32%
Healthcare innovation	30%
Medical innovation	28%
Healthcare innovation	25%
Medical innovation	22%
Healthcare innovation	20%
Medical innovation	18%
Healthcare innovation	15%
Medical innovation	12%
Healthcare innovation	10%
Medical innovation	8%
Healthcare innovation	5%
Medical innovation	3%
Healthcare innovation	2%
Medical innovation	1%
Healthcare innovation	0%

2.2 Overall Study Design

[REDACTED]

[REDACTED]

[REDACTED]

[figure not shown]
[REDACTED]

[REDACTED]

CONFIDENTIAL

Statistical Analysis Plan

Sponsor Name: Akero Therapeutics, Inc.
Sponsor Protocol ID: AK-US-001-0102

2.3 [REDACTED]

CONFIDENTIAL

Statistical Analysis Plan

Sponsor Name: Akero Therapeutics, Inc.
Sponsor Protocol ID: AK-US-001-0102

3. Efficacy and Safety Variables

3.1 Primary Efficacy Endpoint

The primary endpoint is:

- Proportion of subjects who achieve improvement in liver fibrosis, defined as \geq one stage (NASH CRN fibrosis score) and no worsening of steatohepatitis (defined as no increase in NAS for ballooning, inflammation, or steatosis) at Week 24.

3.2 Secondary Efficacy Endpoints

The secondary endpoints are:

- Proportion of subjects who achieve resolution of steatohepatitis (defined as a NAS of 0-1 for inflammation, 0 for ballooning, and any value for steatosis) and no worsening of liver fibrosis as determined by the NASH CRN criteria at Week 24 and Week 96.
- Proportion of subjects who achieve improvement in liver fibrosis by \geq one stage (NASH CRN fibrosis score) and no worsening of steatohepatitis (defined as no increase in NAS for ballooning, inflammation, or steatosis) at Week 96.
- Proportion of subjects who achieve improvement in liver fibrosis by \geq one stage (NASH CRN fibrosis score) at Week 24 and Week 96.
- Change from baseline in hepatic fat fraction measured by MRI-PDFF at Week 24 and Week 96.
- Change from baseline of lipoproteins – Lp (a), total cholesterol, triglycerides, Non-HDL-C, HDL-C, LDL-C, and LDL-P and in markers of lipid metabolism (ApoB and ApoC-III).
- Change from baseline of markers of glycemic control – HbA1c, C-peptide, Adiponectin and HOMA-IR.
- Change from baseline in non-invasive markers of fibrosis – ELF, Pro-C3, C3M, NIS-4 and liver stiffness assessed by transient elastography (FibroScan[®]).
- Change from baseline of body weight.

3.3 Exploratory Efficacy Endpoints

The exploratory endpoints are:

- [REDACTED]
- [REDACTED]
- [REDACTED]
- [REDACTED]

CONFIDENTIAL

Statistical Analysis Plan

Sponsor Name: Akero Therapeutics, Inc.
Sponsor Protocol ID: AK-US-001-0102

3.4 Estimands

In line with ICH E9 (R1) addendum, five attributes (treatment, population, endpoint, intercurrent events, and population-level summary) have been specified to translate the primary efficacy objective into treatment effect that is to be estimated (estimand).

The treatment conditions of interest are EFX 28 mg administered weekly, and EFX 50 mg administered weekly, and are compared with matching placebo administered weekly in addition to standard of care.

CONFIDENTIAL

The population of subjects targeted is adults with NASH with liver fibrosis as defined by the inclusion/exclusion criteria.

The treatment effect is assessed by the primary histological endpoint of improvement in liver fibrosis and no worsening of steatohepatitis at Week 24.

Intercurrent events are handled through a composite strategy (see Table 1).

The population-level summary of the treatment effect will be quantified by comparing observed responder proportions supported by the risk ratio of each investigational product compared to placebo (EFX 28 mg versus placebo or EFX 50 mg versus placebo) calculated from the odds ratio obtained through Cochran-Mantel-Haenszel (CMH) test detailed in the Section 7.6.1.

Table 1 Approach for Intercurrent Events for the Primary Endpoint at Week 24

The estimands attributes for all secondary and exploratory histological endpoints are defined in the same manner as for the primary endpoint described above.

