Table 1. Summary of Week 12 Efficacy Endpoints (Full Analysis Set)

Measure	Placebo (N=21)	EFX (once weekly dose)		
		28 mg (N=19)	50 mg (N=20)	70 mg (N=20)
Absolute reduction in hepatic fat fraction ^a (%)	-0.3	-12.3***	-13.4***	-14.1***
Normalization (<5%) of hepatic fat fraction ^b (%)	5	21	45	50**
Relative reduction in hepatic fat fraction ^a (%)	0	-63***	-71***	-72***
$\geq 30\%$ Relative reduction in hepatic fat fraction ^b (%)	10	84***	85***	75***
$\geq 50\%$ Relative reduction in hepatic fat fraction ^b (%)	5	58**	85***	70***
Reduction in ALT ^a (U/L)	-6	-24***	-30***	-32***

^a Least-squares mean change from baseline

^b Least-squares mean proportion of subjects

** $p < 0.004$, versus placebo

*** $p < 0.001$, versus placebo

Subjects who achieved a $\geq 30\%$ reduction of hepatic fat fraction after 12 weeks treatment, were eligible for a biopsy after 16 weeks treatment. The liver biopsy analysis set included all responders who had Baseline and end-of treatment liver biopsy results. Biopsies were obtained from 2, 13, 13 and 14 subjects respectively for the placebo, 28 mg, 50 mg, and 70 mg treatment groups. Due to COVID-19 and other subject specific issues, biopsies could not be obtained from 8 additional biopsy-eligible subjects, who were all in EFX treatment groups.

A responder based on NAS was defined as a subject with a decrease of ≥ 2 points in NAS with at least 1-point reduction in either lobular inflammation or hepatocellular ballooning with no concurrent worsening of fibrosis stage. In each of the 28 mg and 50 mg groups, 76.9% of subjects were responders. In the 70 mg group, 78.6% of subjects were responders (Table 2). Of the 40 EFX subjects in the Liver Biopsy Evaluable Analysis Set, 53.8%, 76.9% and 35.7% in the 28 mg, 50 mg, and 70 mg EFX groups, respectively, had ≥ 1 stage improvement in fibrosis regression (Table 2). Neither of the placebo responders had regression of fibrosis.

Of the same 40 EFX subjects, a total of 11 (27.5%) achieved ≥ 2 stage improvement in fibrosis regression. This included 4 subjects (30.8%) in the 28 mg group, 5 subjects (38.5%) in the 50 mg group, and 2 subjects (14.3%) in the 70 mg group.

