Resolution of NASH (subjects who had a score of 0-1 for inflammation and 0 for ballooning) without worsening of fibrosis stage was achieved by 46.2%, 53.8%, and 42.9% respectively of the 28-, 50-, and 70-mg groups (Table 2). One of two placebo subjects met this endpoint. Overall, of the 40 EFX subjects, 19 (47.5%) experienced resolution of NASH without worsening of fibrosis stage.

The proportion of subjects who achieved NASH resolution and improvement in fibrosis of ≥ 1 stage was 30.8%, 38.5%, and 14.3% of subjects respectively in the 28-, 50-, and 70-mg EFX groups, respectively. Across the 40 EFX subjects, 11 (27.5%) achieved NASH resolution and improvement of ≥ 1 stage of fibrosis (Table 2). Neither placebo subject met this endpoint.

Overall, 19 (47.5%) subjects achieved improvement in liver fibrosis ≥ 1 stage and no worsening of steatohepatitis. Six (46.2%), 8 (61.5%), and 5 (35.7%) subjects in the 28, 50, and 70 mg EFX groups, respectively, and 0 (0.0%) subjects in the placebo group achieved improvement in liver fibrosis ≥ 1 stage and no worsening of steatohepatitis. Of all EFX-treated subjects, 55.0% experienced fibrosis improvement of ≥ 1 stage.

Table 2. Summary of Histology Endpoints (Liver Biopsy Analysis Set)

Measure (Mean)	Placebo (N=2)	28mg (N=13)	50mg (N=13)	70mg (N=14)
Liver biopsy responders based on NAS system, n (%)	1 (50)	10 (76.9)	10 (76.9)	11 (78.6)
Fibrosis regression of ≥ 1 stage by NASH CRN Classification, n (%) ¹	0 (0)	7 (53.8)	10 (76.9)	5 (35.7)
Fibrosis regression of ≥ 1 stage and no worsening of steatohepatitis	0 (0.0)	6 (46.2)	8 (61.5)	5 (35.7)
Improvement in liver fibrosis ≥ 2 stages (%) ¹	0 (0)	4 (30.8)	5 (38.5)	2 (14.3)
NASH resolution and no worsening of fibrosis stage (%) ¹	1 (50.0)*	6 (46.2)	7 (53.8)	6 (42.3)
NASH resolution AND improvement in fibrosis stage (%) ¹	0 (0)	4 (30.8)	5 (38.5)	2 (14.3)

¹ Liver Biopsy Evaluable Analysis Set (all subjects who had Baseline and end-of-treatment liver biopsy results)

* A single placebo responder lost 25 pounds over 16 weeks (11% weight reduction)

The overall metabolic effect of EFX was impressive, and healthy lipoprotein profiles were restored in subjects presenting with dyslipidemia. Significant changes at Week 16 were

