5.2.2. Dosage and Administration

Detailed information regarding the preparation and administration of EFX or placebo for this study is contained in the EFX Pharmacy Manual. Investigational medicinal product will be administered by subcutaneous injection once weekly as follows:

- Placebo QW (n = 40)
- 28 mg EFX QW (n = 40)
- 50 mg EFX QW (n = 40)

The IMP will be administered by a weekly 1.0 mL subcutaneous injection into the abdomen by a qualified staff member at the clinic or utilizing in-home nursing. The date and time of injection will be recorded. If injection site reactions are observed, mitigation procedures should be put in place as per local standard of care. Examples of mitigations include icing

the injection site, rotating the quadrant of the abdomen in which the injection is administered, or providing antihistamine prior to injection.

If subjects are unable to attend study visits and/or study centers are unable to accommodate on-site visits due to pandemics, natural disasters, or other major disruptions procedures will be put in place to allow for direct-to-subject drug shipments for utilization of in-home nursing, as necessary.

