7.5. Estimands

In line with ICH E9 (R1) addendum, 5 attributes (treatment, population, endpoint, intercurrent events, and population-level summary) have been specified to translate the primary and key secondary efficacy objectives into treatment effects that are to be estimated (estimands).

The treatment conditions of interest are EFX 28 mg administered weekly, and EFX 50 mg administered weekly, and are compared with matching placebo administered weekly.

The treatment effect is assessed by the primary histological endpoint of improvement in liver fibrosis and no worsening of steatohepatitis.

The population of subjects targeted is adults with NASH with liver fibrosis as defined by the inclusion/exclusion criteria.

Intercurrent events are handled through a composite strategy (see Table 6).

The population-level summary of the treatment effect will be quantified by comparing observed responder proportions supported by the risk ratio of investigational product compared to placebo (EFX 28 mg versus placebo or EFX 50 mg versus placebo) calculated from the odds ratio obtained through Cochran-Mantel-Haenszel (CMH) test detailed in the Statistical Analysis Plan.

Table 6. Approach for Intercurrent Events for the Primary Endpoint

Intercurrent Event	Status
Start of additional therapy with potential to impact NASH condition (i.e. rescue medication)	Subject defined as a non-responder (even if a post-treatment biopsy is available)
MELD score ≥ 15	Subject defined as a non-responder (even if a post-treatment biopsy is available)
Hepatic decompensation event	
Unscheduled biopsy showing progression to F4	Subject will be counted as a non-responder
Bariatric surgery	Subject defined as a non-responder

The estimands attributes for all secondary histological endpoints are defined in the same manner as for the primary endpoint described above.

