7.6 Efficacy

Efficacy analysis will be performed by treatment group. In addition, all EFX subjects will be combined as "All EFX" group in all histology analyses and for other efficacy parameters as appropriate.

Note that for analyses using an MMRM model, the model will first use an unstructured covariance matrix. In the event that there are convergence issues, an autoregressive heterogeneous (ARH(1)) covariance structure will be used, followed by autoregressive structure (AR(1)) if convergence issues still exist.

In addition, for analyses using the CMH test, it is noted that the CMH test statistic is not defined in the event there are no responses in one treatment arm and that there may be issues with numerical stability of the estimated odds ratio (and related statistics, e.g. p-values) in the event of few responses within a treatment arm. Therefore, the nominal p-value and corresponding population level summaries will be generated using Fisher's Exact Test on the 2x2 contingency table of an individual active treatment arm (EFX 28mg or EFX 50mg) and Placebo, and the response variable (histology response or non-response) for a given endpoint in the event that there are no responses in a treatment arm for a given population. The analysis with all EFX subjects in a given analysis population will also be generated in this case. Further, in the event of insufficient responses (e.g. less than approximately 3 responses in a given arm) to assess numerical stability of the CMH odds ratio estimate, the Fisher's Exact Test odds ratio estimate and p-value may also be summarized in order to assess the impact of limited responses on the stability of the CMH test.

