7.6.1 Primary Efficacy Analysis

The primary efficacy analysis will be conducted when all the planned subjects complete the 24-Week visit. A CMH test will be used to compare the differences in proportions of subjects who achieve a ≥ 1 -stage improvement in fibrosis compared to baseline without worsening of steatohepatitis between the EFX arms and the placebo arm, adjusting for stratification factors. The analysis will be performed using the LBAS. The point estimates and 95% confidence intervals (CIs) for the differences in proportions will be calculated. The 95% CI will be constructed using the Miettinen and Nurminen method. In addition, the odds ratio and risk ratio point estimate and 95% CI will be summarized for each EFX arm compared to placebo. The Primary efficacy endpoint will be tested at Type I error rate of 0.05, two-sided without adjustment for multiplicity for the comparisons between EFX arms and the placebo arm. P-values will be presented.

CONFIDENTIAL

Statistical Analysis Plan

Sponsor Name: Akero Therapeutics, Inc.
Sponsor Protocol ID: AK-US-001-0102

The same analysis will be repeated on the PPS and FAS. For any subjects in the FAS with a missing efficacy value, the efficacy variable will be considered as non-responder.

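### The risk ratio supporting the primary estimand is to be derived from the CMH odds ratio, with no CI method named; a direct Mantel-Haenszel risk ratio with a named interval is better and costs little.

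*SAP*

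**What the plan says.** SAP 3.4 makes the comparison of observed responder proportions the population-level summary. A risk ratio for each EFX dose against placebo supports it, "calculated from the odds ratio obtained through Cochran-Mantel-Haenszel (CMH) test detailed in the Section 7.6.1". Protocol 7.5 has the same rule and leaves the detail to the SAP: "calculated from the odds ratio obtained through Cochran-Mantel-Haenszel (CMH) test detailed in the Statistical Analysis Plan".

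SAP 7.6.1 adds only that "the odds ratio and risk ratio point estimate and 95% CI will be summarized for each EFX arm compared to placebo". It gives no conversion formula, does not say which placebo risk enters it, and names no variance. Miettinen-Nurminen is named there, but for the difference in proportions; the odds ratio and risk ratio come in a separate sentence further on.

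SAP 3.4 carries the same attributes over to the secondary and exploratory histological endpoints. SAP 7.6.2.1 to 7.6.2.3, 7.6.3.1 and 7.6.3.3 repeat the risk-ratio wording.

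For sparse data, SAP 7.6 notes that "the CMH test statistic is not defined in the event there are no responses in one treatment arm". In that case it takes the p-value and the matching population-level summaries from Fisher's exact test on the unstratified 2x2 table.

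**The concern.** An odds ratio fixes a risk ratio only once a placebo risk is supplied. Two consequences follow.

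1. **Point estimate.** A stratum-adjusted odds ratio is a conditional quantity, while the pooled placebo proportion is a marginal one. Combining them is harmless when the strata have the same risk and pushes the ratio upward when they do not.
2. **Interval.** The obvious shortcut converts the two odds-ratio limits at the observed placebo proportion. That treats the proportion as known, so the interval is too narrow when the effect is large, mainly because its upper limit is too low.

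At stake is the accuracy of a reported effect size and its interval, for the primary endpoint and for every histological endpoint that inherits the estimand.

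**Working it through.** There is no figure in the plan to reproduce: no risk ratio is stated and the planning rates are redacted.

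**Inputs**
- Arm size 40: "28 mg EFX QW (n = 40" and likewise for the other arms (Protocol 5.2.2).
- Four strata: T2D status by fibrosis stage (Protocol 3.1), taken as equal in size (assumption).
- Placebo rate: assumed 20%, range 10-30%.
- Higher EFX rates: phase 2a, "Six (46.2%), 8 (61.5%), and 5 (35.7%) subjects in the 28, 50, and 70 mg EFX groups" (Protocol 1.4.1.3), so 6/13 = 46.2% and 8/13 = 61.5%. Those subjects had a fat response first: with at least a 30% "reduction of hepatic fat fraction after 12 weeks treatment, were eligible for a biopsy after 16 weeks treatment". These rates may be too high here.
- Lower EFX rates: the same responders over the phase 2a full analysis set, 6/19 = 31.6% and 8/20 = 40%, counting unbiopsied subjects as non-responders. These may be too low.

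**Formulas**
- Conversion: RR = OR / (1 - p0 + p0 x OR).
- Direct: Mantel-Haenszel common risk ratio with Greenland-Robins variance.

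**Unstratified example, 16/40 against 8/40**
- OR = (16 x 32)/(24 x 8) = 2.67. SE of log OR = sqrt(1/16 + 1/24 + 1/8 + 1/32) = 0.510, giving limits 0.98 and 7.25.
- At p0 = 0.20 the point estimate is 2.67/(0.8 + 0.2 x 2.67) = 2.00. The upper limit is 7.25/(0.8 + 0.2 x 7.25) = 3.22 and the lower is 0.98.
- Direct: RR 2.00, SE of log RR = sqrt(1/16 - 1/40 + 1/8 - 1/40) = 0.371, CI 0.97-4.14.
- For 25/40 against 8/40 the converted CI is 1.89-4.10 and the direct CI 1.61-6.07.

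**Stratified example, EFX 5, 5, 7, 8 and placebo 1, 1, 3, 3, each of 10**
- MH OR = (45 + 45 + 49 + 56)/(5 + 5 + 9 + 6) = 195/25 = 7.80.
- Converted at the pooled p0 of 0.20: 7.80/(0.8 + 1.56) = 3.31. Direct: 25/8 = 3.12. The converted value is about 6% higher (3.31/3.12 = 1.06).

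**Point estimate in simulation.** With equal stratum risks the median ratio of converted to direct is 1.00; at 20% placebo its 5th-95th percentiles are 0.96-1.04 to 0.94-1.07. With placebo risks of 10, 15, 25 and 25% in unequal strata (7, 7, 13, 13 per arm) the median is 1.02-1.03. Across the assumed unequal-risk scenarios tried, the median excess is about 1-15%.

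**Coverage of a nominal 95% CI**, 40,000 trials per scenario, equal stratum risks, limits converted at the observed placebo proportion:

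| EFX rate | Placebo 10% | Placebo 20% | Placebo 30% | Upper limit below truth, placebo 20% |
|---|---|---|---|---|
| 31.6% | 91.4% | 93.0% | 94.9% | 4.3% |
| 40% | 87.0% | 89.8% | 92.9% | 6.6% |
| 46.2% | 83.3% | 86.3% | 90.6% | 9.1% |
| 61.5% | 71.5% | 74.2% | 80.1% | 17.6% |

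The direct interval covers 95.3-96.8% throughout. With 32 per arm, allowing for missing biopsies, the converted figures are similar (72.5-95.1%). At RR = 1 converted coverage is 95.4-98.6%. The converted interval excluded 1 exactly when the odds-ratio interval did.

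**Zero placebo responders.** The probability is (1 - p0)^n. At 10% and n = 40 it is 0.9^40 = 1.5%; at n = 32 it is 3.4%. For an endpoint with an assumed 5% placebo rate it is 0.95^40 = 13% and 0.95^32 = 19%. In these trials the risk ratio has no finite value, from the 2x2 table or otherwise.

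**The case against.** The strongest reply is that the under-coverage belongs to a procedure the plan never states. A reader might infer that the SAP prescribes converted limits. It does not: a direct stratified interval, or one that allows for error in the placebo proportion, would also fit SAP 7.6.1, and then no coverage is lost. The table shells mentioned in SAP 7.1 were not available and may name the method. This stands, and it makes the coverage figures conditional. It does not rescue the point estimate, which both documents do tie to the odds ratio.

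A reader might also infer that the conversion cannot be done for want of a placebo risk. That goes too far. The same sentence of SAP 3.4 speaks of observed responder proportions, so the observed placebo proportion is the natural choice. What is missing is whether it is pooled or stratum-weighted, and with equal stratum risks the choice hardly matters.

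Nor is SAP 7.6 silent on an arm without responders, since it sends the population-level summaries to the 2x2 table. That rule simply cannot yield a finite risk ratio when the empty arm is placebo. With no EFX responders the ratio is 0 and is defined.

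Finally, the 61.5% rate comes from 13 subjects eligible for biopsy only after a fat response. At 31.6% the coverage loss is small, and it is negligible against 30% placebo.

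**Conclusion.** The point holds as a minor one. The stated route, from CMH odds ratio to risk ratio, is a weaker method than estimating the risk ratio directly, and its interval is unspecified. The point estimate is close to the direct one when strata have equal risk and a median of about 1-15% too high in assumed scenarios where they differ. If the limits are converted at the observed placebo proportion, coverage is about 74-93% at 20% placebo, against about 96% direct. These figures rest on 40 per arm, four equal strata and assumed response rates.

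A reader might take this as a threat to the primary conclusion. The documents do not support that. The risk ratio is a supporting summary; the CMH p-value and the risk-difference CI do not depend on it, and coverage at RR = 1 is not impaired.

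**What to change.** - **SAP 3.4:** replace the derivation from the odds ratio with the Mantel-Haenszel common risk ratio, estimated directly from the tables stratified by T2D status and fibrosis stage. Align Protocol 7.5 at its next amendment; it already leaves the detail to the SAP.
- **SAP 7.6.1, and the matching histological endpoints in 7.6.2 and 7.6.3:** name the risk-ratio CI, for example Greenland-Robins or a stratified score interval.
- **SAP 7.6:** add that with zero placebo responders no risk-ratio point estimate is reported and the risk difference with its CI is given, or that a score lower limit is used.

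The cost is a few sentences, using the same stratified tables as the CMH test. The downside is a wider risk-ratio interval. It is also a documented SAP change. The current SAP is Version 3 of 07 Feb 2024, and its Section 8 describes dose assignment to Week 96 in the past tense, so the Week 24 unblinding may already have taken place. A change made after that should be labelled as such.
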